# 11.1.4 Significant Adverse Events

Other significant AEs are defined as marked hematological and other laboratory abnormalities (other than those meeting the definition of serious) and any events that led to an intervention, including withdrawal of test drug, dose reduction, or significant additional concomitant therapy.

# 11.1.5 Treatment-Emergent Adverse Events

An AE is defined as treatment emergent if the first onset or worsening is after the first administration of IP (NFC-1 or placebo) and not more than 7 days after the last administration of IP.

# 11.2 Management of Adverse Events

Adverse events will be collected from the time of signing informed consent form (ICF) through the Follow-up Visit or Early Termination Visit, whichever occurs first.

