If the subject experiences unacceptable intolerability, in the opinion of the investigator, the dose may be reduced (if available) by 1 dose level (to the previous dose). If the subject tolerates the dose reduction well and maintains symptom control, the subject may be maintained at that reduced dose for the remainder of the optimization period (through Visit 6).

Only 1 dose reduction is permitted during the optimization period. Visit 5 will be the last visit at which titration can occur. Once a subject has reached an optimal dose, this dose will be maintained for the remainder of the dose-optimization phase of the study (through Visit 6). Subjects who are unable to tolerate the IP will be discontinued. After the dose optimization period, subjects will continue to receive the current optimized dose of IP for an additional 2 weeks. A 7-day follow-up call will occur after discontinuing study treatment.

Subjects who discontinue because they are unable to tolerate the IP must complete all early termination (ET) visit assessments required during the last study visit. These subjects will also receive a 7-day follow-up call after discontinuing study treatment.

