#### 10. STUDY PROCEDURES

Subjects will provide written informed consent before any study-related procedures are initiated, including the cessation of prohibited concomitant therapy.

For the timing of assessments and procedures throughout the study, refer to the schedule of events (Section 17.1). Throughout the study, every reasonable effort should be made by study personnel to follow the timing of assessments and procedures in the schedule of events for each subject. If a subject misses a study visit for any reason, the visit should be rescheduled as soon as possible, ideally within 2 days of the originally scheduled date.

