## 10.1.4 7-day Follow-up Call

At Day 49 (+ 5 days), caregivers will receive a telephone call to assess and record concomitant medication and newly occurring AEs since the last evaluation.

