### 11.2.3 Documentation

All AEs occurring within the period of observation for the study must be documented in the eCRF with the following information, where appropriate. The period of observation for the study is described in Section 11.2.

- AE name or term.
- When the AE first occurred (start date and time).
- When the AE stopped (stop date and time or an indication of "ongoing").
- Severity of the AE.
- Seriousness (hospitalization, death, etc.).
- Actions taken.
- Outcome.
- Investigator opinion regarding the AE relationship to the IP.

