# 11.2.5 Follow-up

Any AE will be followed (up to a maximum of 7 days after the last dose of the IP) to a satisfactory resolution, until it becomes stable, or until it can be explained by another known cause(s) (ie, concurrent condition or medication) and clinical judgment indicates that further evaluation is not warranted. All findings relevant to the final outcome of an AE must be reported in the subject's medical record and recorded on the appropriate eCRF.

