Abbreviations: ADHD-RS-5 = Attention Deficit Hyperactivity Disorder Rating Scale Version 5, ASHS = Adolescent Sleep Hygiene Scale, CGI-I = Clinical Global Impression of Improvement, CGI-S = Clinical Global Impression of Severity, C-SSRS = Columbia Suicide Severity Rating Scale, ECG = electrocardiogram, ET = early termination, IQ = intelligence quotient, IWRS = interactive web response system, K-SADS-PL = Kiddie Schedule for Affective Disorders and Schizophrenia - Present and Lifetime Version, SCARED = Screen for Childhood Anxiety-related Emotional Disorders, WASI-II = Wechsler Abbreviated Scale of Intelligence, second edition

- a Caregivers will receive a follow-up telephone call from a study staff member 7 days after the last visit to collect information about any ongoing AEs and concomitant medication.
- b Informed consent to be completed by a duly authorized subject representative. Assent is to be provided by subject where required.
- c Medical and medication history including confirmation from the sponsor that each subject has been determined to have disruptive mutations in genes within the GRM-network as determined by the presence of CNVs (GRM biomarker-positive subjects).
- d The CGI–S rates illness severity on the following 7-point scale: 1 = normal, not at all ill, 2 = borderline mentally ill, 3 = mildly ill, 4 = moderately ill, 5 = markedly ill, 6 = severely ill, and 7 = among the most extremely ill subjects.
- e The CGI-I requires the investigator to assess how much the subject's illness has improved or worsened: 1 = very much improved, 2 = much improved, 3 = minimally improved, 4 = no change, 5 = minimally worse, 6 = much worse, and 7 = very much worse.
- f IWRS will assign treatment numbers and will also manage all logistical aspects of treatments (eg, drug resupply and expiry dates).
- g If more than 23 days have elapsed between the Screening Visit and the Baseline Visit clinical laboratory tests, serum pregnancy test, vital signs and weight, urine drug test, and ECG must be repeated and the results available and reviewed prior to proceeding with the Baseline Visit.

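### Protocol 11.2 ends AE collection at the Early Termination visit although the schedule of events records AEs at a later call, and SAP 6.2 dates an AE with unknown start month to the day before first dose; both effects are small

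*Protocol*

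**What the plan says.** **AE collection period.** Protocol 11.2 runs AE collection from informed consent "through the Follow-up Visit or Early Termination Visit, whichever occurs first". Section 11.2.3 makes this the recording duty: "All AEs occurring within the period of observation for the study must be documented in the eCRF", with the period taken from 11.2.

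**The call after the last visit.** The schedule of events (Protocol 17.1) ticks the adverse-event row at the follow-up call, in the column after Visit 8/ET. Its footnote a places the call "7 days after the last visit to collect information about any ongoing AEs and concomitant medication". Section 10.1.4, written for Day 49 (+5 days), says "caregivers will receive a telephone call to assess and record concomitant medication and newly occurring AEs since the last evaluation". Section 9.9, on subjects who stop because they cannot tolerate the product, requires the ET assessments and adds: "These subjects will also receive a 7-day follow-up call after discontinuing study treatment".

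**TEAE window.** Protocol 11.1.5, repeated in SAP 6.3, counts an event if onset or worsening is after the first administration and "not more than 7 days after the last administration of IP".

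**Partial AE start dates.** SAP 6.2, applied to AEs by SAP 9.1, imputes the randomization date when the start month is unknown and the year is the randomization year. When only the day is unknown and the month matches, it uses the day of first dose. The same section imputes missing severity as severe and missing causality as related. Protocol 7.1 and 10.1.2 place randomization on the day before first dose.

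**Table shell.** The note to SAP Table 14.3.1.2 counts onset at or after the start of treatment and gives no upper limit.

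**The concern.** Obtaining additional safety data is one of the trial's two objectives, and the TEAE tables are its main AE summaries. Each rule can keep an event out of those tables although it belongs there.

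- A new event reported at the planned call by a subject who stopped early can fall inside the TEAE window, yet lie outside the period that 11.2 and 11.2.3 require to be recorded. A site or monitor would have a literal reason not to enter it.
- An event known only to have started in the randomization year is dated before treatment, so by onset it is not treatment-emergent. It stays in Listing 16.2.6.1 but leaves the summaries. This runs against the cautious direction of the severity and causality rules in the same SAP section.

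Efficacy, power and type I error are not involved.

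**Working it through.** The plan gives no figure to reproduce. The check compares the passages and then bounds the two effects.

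**Part 1: the collection cut-off**

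An early terminator reaches the ET visit before any follow-up contact, so the rule in 11.2 selects the ET visit. The contradiction rests on the AE tick at the call in the schedule of events, read with 10.1.4, which asks for new events. Section 9.9 shows that some early terminators are meant to get the call, but does not say what it records. Footnote a mentions only ongoing events.

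Inputs:
- Planned non-completers: 90 − 80 = 10 (Protocol 13.2).
- TEAE window per subject: days on product + 7 (Protocol 11.1.5).
- Completers: 80 × (42 + 7) = 3,920 subject-days.
- Non-completers, assuming they stop between day 7 and day 35: 10 × (7 + 7) = 140 to 10 × (35 + 7) = 420.
- Total: 4,060 to 4,340 subject-days.

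Loss = k × (7 − L). Here k is the number of early terminators whose AE recording stops at an ET visit, and L is the days from last dose to that visit. Both are assumptions.

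| k | L | Loss (subject-days) | Share of TEAE-window days |
|---|---|---|---|
| 10 | 0 | 70 | 1.61 to 1.72% |
| 10 | 2 | 50 | 1.15 to 1.23% |
| 5 | 0 | 35 | 0.81 to 0.86% |
| any | 7 | 0 | 0 |

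**Part 2: the unknown-month rule**

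Example: randomized 15 Nov 2016, first dose 16 Nov 2016, AE start recorded only as 2016. The imputed start is 15 Nov 2016, one day before first dose.

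Enumeration on an illustrative calendar: randomization on each of the 731 days of 2016–2017, first dose the next day, true onset on any of the 49 days from first dose. This gives 731 × 49 = 35,819 cases.

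- Onsets in the calendar year after randomization: 49 + 48 + … + 1 = 1,225 at each of two year-ends, 2,450 in all.
- Remaining cases: 35,819 − 2,450 = 33,369 (93.2%). All are imputed before first dose. This percentage is therefore just the share of onsets in the same calendar year as randomization.
- Unknown-day rule, same cases: 0 imputed before first dose.
- Unknown-month rule re-anchored to first dose: 0 imputed before it, and 33,467 (93.4%) exactly on it. A strict reading of onset after first administration would still exclude these, so the fix must say how they count.

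Frequency: AEs are asked about weekly. A 7-day interval between visits straddles a month end in 24 month ends × 6 start days × 6 weeks = 864 of 731 × 6 = 4,386 cases (19.7%). This shows how often the month could be in doubt if only the interval were known. It is not a rate of missing months.

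**The case against.** **On the cut-off.** The strongest reply is that sites work from the schedule of events. Protocol 10 says "every reasonable effort should be made by study personnel to follow the timing of assessments and procedures in the schedule of events", and there AEs are ticked at the call. Section 7.1 documents AEs through a post-treatment visit, though it does not define that visit. Section 11.2.5 follows existing AEs for up to 7 days after last dose, and 11.2.6.1 states no ET cut-off for serious events. All of this stands and limits the loss mainly to new non-serious events. It does not remove the conflict, because 11.2 is the section that defines the period and following a known event is not collecting a new one.

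A reader might infer that 9.9 or footnote a contradicts 11.2 on its own. Neither does: continued follow-up of ongoing events after ET is compatible with 11.2.

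**On the date rule.** It contradicts no other passage; it is a weakness of derivation. Start date and time are collected, so a known year with an unknown month should be very rare. The comparison with the unknown-day rule also depends on the one-day gap: with an assumed two-day gap, that rule places 707 of 35,819 cases (2%) before first dose. These points stand and keep the matter small, but the written rule still gives the wrong class whenever it is used for an on-treatment onset in the randomization year.

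**On the wording.** It is tempting to align the TEAE definition with the shell note. That would drop the 7-day upper limit, put the SAP at odds with Protocol 11.1.5, and risk counting events timed before dosing on the first-dose day.

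**Conclusion.** Minor, and wrong as written in two places.

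1. Protocol 11.2, and 11.2.3 through it, conflicts with the schedule of events read with 10.1.4. The loss is zero where sites follow the schedule. The ceiling is about 70 subject-days, or 1.6 to 1.7% of TEAE-window time. It assumes that all 10 planned non-completers have an ET visit on the day of last dose and nothing is recorded afterwards. The true figure is lower if some are lost or withdraw consent without an ET visit, or if the call is made and recorded.
2. The unknown-month rule in SAP 6.2 dates every same-year case to the day before first dose, so by onset it is never treatment-emergent. Very few such records are expected.

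A reader might infer that every early terminator loses a week of safety data, that 93% of partially dated AEs will be lost, or that the safety comparison is biased towards one arm. The documents support none of these. The first ignores the schedule. The second takes a calendar share for a frequency. For the third, nothing in the plan shows that either rule acts differently by arm.

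**What to change.** **Protocol 11.2 and 11.2.3.** Reconcile with 9.9, 10.1.4 and 17.1, so that AE collection for dosed subjects, including early terminators, runs through the follow-up call already scheduled, except where consent is withdrawn or the subject is lost to follow-up. State that the call records both ongoing and new AEs.

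**SAP 6.2, AE start dates only.** When the month is unknown and the year is that of first dose, impute the first-dose date unless the recorded AE end date precedes first dose. State that an AE whose imputed start equals the first-dose date is treated as treatment-emergent. Leave the medication rules alone: re-anchoring them would remove prior status from an ongoing medication with unknown start month in that year.

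**TEAE definition.** Leave Protocol 11.1.5 and SAP 6.3 unchanged, including the 7-day limit, and correct the Table 14.3.1.2 note to match them. Log the changes in SAP section 10.

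**Cost.** A short protocol amendment, signed by investigators and approved by the IRB (Protocol 14.8 and 15.3), and a small SAP edit. No visit or call is added. A rare AE that truly began before dosing, with unknown month and no end date before first dose, may be counted as a TEAE. That is the same cautious direction as the severity and causality rules.

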# 11.2.1 Collection

The investigator is responsible for the detection and documentation of events meeting the criteria and definition of an AE or SAE described previously. At each visit, the subject will be allowed time to spontaneously report any issues since the last visit or evaluation. The investigator will then monitor and/or ask about or evaluate AEs using nonleading questions, such as:

- "How are you feeling?"
- "Have you experienced any issues since your last visit?"
- "Have you taken any new medications since your last visit?"

Any clinically relevant observations made during the visit will also be considered AEs.

### 11.2.2 Evaluation

# 11.2.2.1 Severity of Adverse Events

The clinical severity of an AE will be classified as:

Mild: Usually transient and may require only minimal treatment or therapeutic

intervention. The event does not generally interfere with usual activities of

daily living.

Moderate: Usually alleviated with additional specific therapeutic intervention. The

event interferes with usual activities of daily living, causing discomfort but

poses no significant or permanent risk of harm to the subject.

27 Oct 2016 AD-MW-07.04 29-Mar-2013 Version: Final Version v4.0 Page 38 of 58

Severe: Interrupts usual activities of daily living, or significantly affects clinical

status, or may require intensive therapeutic intervention.

It is important to distinguish between severe AEs and SAEs. Severity is a classification of intensity whereas an SAE is an AE that meets serious criteria, as described in Section 11.1.3.

### 11.2.2.2 Seriousness

The investigator is to evaluate whether the AE meets serious criteria, as described in Section 11.1.3.

# 11.2.2.3 Action(s) Taken

Action(s) taken may consist of:

Dose increased: An indication that a medication schedule was modified by addition;

either by changing the frequency, strength or amount.

Dose not changed: An indication that a medication schedule was maintained.

Dose reduced: An indication that a medication schedule was modified by subtraction,

either by changing the frequency, strength or amount.

Drug interrupted: An indication that a medication schedule was modified by temporarily

terminating a prescribed regimen of medication.

Drug withdrawn: An indication that a medication schedule was modified through

termination of a prescribed regimen of medication.

Not applicable: Determination of a value is not relevant in the current context.

Unknown: Not known, not observed, not recorded, or refused.

### 11.2.2.4 Outcome at the Time of Last Observation

The outcome at the time of last observation will be classified as:

- Recovered/resolved.
- Recovered/resolved with sequelae.
- Recovering/resolving.
- Not recovered/not resolved.
- Fatal\*.
- Unknown

\*Only select fatal as an outcome when the AE results in death. If more than one AE is possibly related to the subject's death, the outcome of death should be indicated for each such AE. Although "fatal" is usually an event outcome, events such as sudden death or unexplained death should be reported as SAEs.

# 11.2.2.5 Adverse Event Relationship to Investigational Product

The investigator must make an assessment of each AE's relationship to the IP. The categories for classifying the investigator's opinion of the relationship are listed below.

Not related: An AE with sufficient evidence to accept that there is no causal

relationship to IP administration (eg, no temporal relationship to drug administration, because the drug was administered after onset of event;

investigation shows that the drug was not administered; another cause was

proven).

Unlikely related: An AE, including laboratory test abnormality, with a temporal

relationship to IP administration that makes a causal relationship improbable, and in which other drugs, events or underlying disease

provide plausible explanations.

Possibly related: An AE with a reasonable time sequence to administration of the IP, but

which could also be explained by concurrent disease or other drugs or events. Information on drug withdrawal may be lacking or unclear.

Related: An AE occurring in a plausible time relationship to IP administration, and

which cannot be explained by a concurrent disease or other drugs or events. The response to withdrawal of the drug (dechallenge) is clinically

reasonable.

The AE relationship to IP will be assessed separately by the investigator and Medgenics.

### 11.2.3 Documentation

All AEs occurring within the period of observation for the study must be documented in the eCRF with the following information, where appropriate. The period of observation for the study is described in Section 11.2.

- AE name or term.
- When the AE first occurred (start date and time).
- When the AE stopped (stop date and time or an indication of "ongoing").
- Severity of the AE.
- Seriousness (hospitalization, death, etc.).
- Actions taken.
- Outcome.
- Investigator opinion regarding the AE relationship to the IP.

### 11.2.4 Treatment of Adverse Events

Adverse events that occur during the study will be treated, if necessary, by established standards of care. If such treatment constitutes a deviation from the protocol, the subject may continue in the study/should be withdrawn from the study and the reason must be documented in the eCRF. The decision about whether the subject may continue in the study will be made by the sponsor after consultation with the investigator and/or medical monitor.

If AEs occur in a subject that are not tolerable, or for which continued administration of IP is not reasonable in view of the potential benefit to subject, the investigator must decide whether to stop the study and/or treat the subject. Special procedures may be recommended for the specific IP, such as the collection of a serum sample for blood concentrations of IP, specific tapering procedures, or treatment regimens, as appropriate.

For double- or triple-blinded studies, it is not necessary to unblind a subject's treatment assignment in most circumstances, even if an SAE has occurred. If unblinding is necessary, see Section 9.6 for a description of the unblinding procedures.

Version: Final Version v4.0 Page 40 of 58

# 11.2.5 Follow-up

Any AE will be followed (up to a maximum of 7 days after the last dose of the IP) to a satisfactory resolution, until it becomes stable, or until it can be explained by another known cause(s) (ie, concurrent condition or medication) and clinical judgment indicates that further evaluation is not warranted. All findings relevant to the final outcome of an AE must be reported in the subject's medical record and recorded on the appropriate eCRF.

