## 8.3 Premature Subject Withdrawal

All subjects will be advised that they are free to withdraw from participation in this study at any time, for any reason, and without prejudice. Every reasonable attempt should be made by the investigator to keep subjects in the study; however, subjects must be withdrawn from the study if they withdraw consent to participate. Investigators must attempt to contact subjects who fail to attend scheduled visits by telephone or other means to exclude the possibility of an AE being the cause of withdrawal. Should this be the cause, the AE must be documented, reported, and followed as described in Section 11.2.

The sponsor reserves the right to request the withdrawal of a subject due to protocol violations or other reasons.

The investigator also has the right to withdraw subjects from the study at any time for lack of therapeutic effect that is intolerable or otherwise unacceptable to the subject, for intolerable or unacceptable AEs, intercurrent illness, noncompliance with study procedures, administrative reasons, or in the investigator's opinion, to protect the subject's best interest.

If a subject is withdrawn before completing the study, the reason for withdrawal and the date of discontinuation will be recorded on the appropriate electronic case report form (eCRF). Whenever possible and reasonable, the evaluations that were to be conducted at the completion of the study should be performed at the time of premature discontinuation.

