## 10.3.3.1.4 Evaluation of Laboratory Values

The normal ranges of values for the laboratory assessments in this study will be provided by the responsible laboratory and submitted to Medgenics, Inc. prior to the beginning of the study. They will be regarded as the reference ranges on which decisions will be made.

If a laboratory value is out of the reference range, it is not necessarily clinically relevant. The investigator must evaluate the out-of-range values and record his/her assessment of the clinical relevance in the appropriate eCRF.

All laboratory values which, in the investigator's opinion, show clinically relevant or pathological changes during or after termination of the treatment are to be discussed with the medical monitor and reported as AEs and followed, as described in Section 11.2.5.

All measurements described in this section are recognized standard methods.

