## 10.3.3.2.2 Electrocardiogram

A standard 12-lead ECG will be performed after the subject has been supine for at least 5 minutes. All ECG recordings will be identified with the subject number, subject initials, date, and time of the recording and will be attached to the subject's eCRF.

All ECG values which, in the investigator's opinion, show clinically relevant or pathological changes during or after termination of the treatment are to be discussed with the medical monitor and reported as AEs and followed, as described in Section 11.2.5.

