## 11.3 Special Considerations

# 11.3.1 Adverse Events of Special Interest

The following events will be considered as AEs of special interest during this study:

- Psychosis.
- Suicidal ideation.

Based on the population under study, and their age, suicidal ideation will be considered as an AE of special interest.

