# 11.3.2 Pregnancy

All women of childbearing potential who participate in the study should be counseled on the need to practice adequate birth control and on the importance of avoiding pregnancy during study participation. Women should be instructed to contact the investigator or study staff immediately if pregnancy occurs or is suspected.

Pregnancy testing will be conducted prior to administration of IP on every woman of childbearing potential. A woman who is found to be pregnant at the Screening Visit will be excluded from the study and considered to be a screening failure.

A woman who becomes pregnant during IP treatment or within 30 days of discontinuing the IP will be immediately discontinued from study participation. The investigator must report the pregnancy within 24 hours of learning of the pregnancy to Pharmacovigilance using the Pregnancy Data Collection Form via the same fax and email address as for SAE reporting. The investigator should contact the designated individual(s) who receive SAE notification and record information related to the pregnancy on an Exposure in Utero form/other designated form provided by the sponsor or its designee.

Early Termination Visit assessments are required as soon as possible after learning of the pregnancy. The investigator is also responsible for following the pregnancy until delivery or termination. These findings must be reported on the Exposure in Utero Form/other designated form and forwarded to the designated individual(s). The event meets the SAE criterion only if it results in a spontaneous abortion or a congenital anomaly.

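### Protocol 11.2.5 stops required follow-up of every AE 7 days after the last dose, with no exception for SAEs, AEs of special interest or clinically relevant laboratory or ECG abnormalities

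*Protocol*

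**What the plan says.** Protocol 11.2.5 sets one rule for all adverse events: "Any AE will be followed (up to a maximum of 7 days after the last dose of the IP) to a satisfactory resolution". Follow-up may also end when the event is stable, or when it has another known cause and further evaluation is judged unnecessary. All of these end points sit inside the 7-day limit.

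Other sections rely on that rule:

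- Protocol 10.3.3.1.4: clinically relevant laboratory changes "are to be discussed with the medical monitor and reported as AEs and followed, as described in Section 11.2.5".
- Protocol 10.3.3.2.2: clinically relevant ECG changes are to be "reported as AEs and followed, as described in Section 11.2.5".
- Protocol 8.3: where an AE causes withdrawal, "the AE must be documented, reported, and followed as described in Section 11.2".
- Protocol 11.3.1 names psychosis as an AE of special interest and adds that "suicidal ideation will be considered as an AE of special interest", but gives neither a follow-up period.
- Protocol 11.2.6.1 requires SAE reporting within 24 hours and later forwarding of additional information. It sets no duty to follow the subject to an outcome.

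Only pregnancy has a longer period: "The investigator is also responsible for following the pregnancy until delivery or termination" (Protocol 11.3.2).

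The one scheduled contact after treatment is the 7-day call. In Protocol 10.1.4, "caregivers will receive a telephone call to assess and record concomitant medication and newly occurring AEs since the last evaluation". Footnote a of the schedule in 17.1 describes its purpose as "to collect information about any ongoing AEs and concomitant medication". No laboratory test, ECG or C-SSRS is scheduled with it. Protocol 11.2 ends AE collection at the follow-up contact or the early termination visit, whichever is first.

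**The concern.** A 7-day limit is reasonable for a routine headache. It is a poor fit for the few events on which the safety conclusions would turn: an SAE, new psychosis or suicidal ideation in an adolescent, or a liver enzyme or creatine kinase rise found at the end of treatment. If such an event is open on day 7, the site may record it as ongoing and has met the protocol. Obtaining safety data in this population is one of the two study objectives (Protocol 6), and no data safety monitoring board is planned (Protocol 12). What is at stake is whether the study report can say how these events ended.

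**Working it through.** No statistical figure is involved. The check is to look for an exception to the cap, then to count the days it leaves.

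**Is there an exception?** Protocol 8.3, 10.3.3.1.4 and 10.3.3.2.2 point into Section 11.2 or 11.2.5 and set no period of their own. Section 11.3.1 is silent on duration. Section 11.2.6.1 concerns passing information on. The second sentence of 11.2.5 asks that findings bearing on the final outcome be recorded, but does not oblige anyone to obtain them after the limit. The SAP adds no follow-up rule. Pregnancy is the only exception.

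**Days remaining after the last dose.** For an event that starts or is first seen *k* days after the last dose, required follow-up is at most 7 − *k* days.

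| Case | *k* | Days left |
|---|---|---|
| Visit 8 on the last dosing day | 0 | 7 |
| Visit 8 on Day 44, dosing stopped on Day 42 | 2 | 49 − 44 = 5 |
| Event 5 days after last dose | 5 | 2 |
| Event 7 days after last dose | 7 | 0 |
| Post-treatment AE (SAP 6.3), up to the latest call | 8 to 12 | none |

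The treatment-emergent window in Protocol 11.1.5 also closes at 7 days. An event on day 7 is therefore treatment-emergent with no required follow-up.

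**Events found during treatment.** With the last dose on Day 42 the cap falls on Day 49. An event seen on Day 14 has up to 49 − 14 = 35 days, and one seen on Day 28 has up to 49 − 28 = 21 days. ECG and C-SSRS are done at every visit from Visit 3 to Visit 8 (Protocol 10.1.3.1, 10.1.3.2), so those findings can surface weekly.

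**Laboratory findings.** On treatment, the protocol schedules laboratory tests only at Visit 3 and Visit 8/ET. At Visit 3 (Day 7) the first dose increase has not yet been taken, so every subject is still on 100 mg twice daily. For completers the next scheduled test is nominally 42 − 7 = 35 days later. An abnormality arising at 200 or 400 mg twice daily is thus first seen by scheduled testing at Visit 8, with 5 to 7 days left at sampling. The documents give no laboratory turnaround. If it is 1 to 3 days (assumption), 5 − 3 = 2 to 7 − 1 = 6 days remain once the result is known. SAP Table 1 ticks laboratory tests at every visit from Baseline. If sites worked that way, detection would be earlier, but the protocol's text and schedule do not require it.

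**The call.** Protocol 10.2 places it 7 to 12 days after the last dose, which is 7 − 7 = 0 to 12 − 7 = 5 days after the cap. By the study days in 10.1.4 (Day 49 to 54), a subject whose last dose was on Day 40 reaches the cap on Day 47 and is called 49 − 47 = 2 to 54 − 47 = 7 days after it.

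**The case against.** The strongest case is that the limit is a deliberate choice with little consequence. Protocol 9.7 gives a half-life of about 4 hours, so 7 days is 168 / 4 = 42 half-lives. Most drug effects that reverse quickly will have done so by then. This stands for many events, but not for abnormalities that resolve slowly after the drug has gone, and those are the ones a cap cuts off.

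Several stronger readings are tempting, and the documents do not support them.

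- *A reader might infer that the cap spoils causality assessment*, because Protocol 11.2.2.5 mentions response to withdrawal under 'Related'. The next category, 'Possibly related', expressly allows for withdrawal information that is missing or unclear, and SAP 6.3 and 9.1 pool the two. An event that drops one category for this reason changes no planned table of related AEs.
- *A reader might infer that all important safety signals surface too late.* Late detection applies mainly to laboratory tests. ECG and C-SSRS are repeated at every treatment visit.
- *A reader might infer that care, or SAE information, stops at day 7.* Protocol 11.2.4 provides treatment by standard of care, 10.3.3.1.4 and 10.3.3.2.2 bring in the medical monitor, and 9.13 funds up to 3 months of after-care. Protocol 11.2.6.1 sets no time limit on forwarding SAE information or on pharmacovigilance requests. None of this obliges the study to follow the event and record its end.

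The outcome list in 11.2.2.4 includes a not-resolved category, so the case report form can always be completed. That makes the rule workable, but the outcome stays unknown.

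**Conclusion.** The point holds as a gap in safety documentation. SAEs, AEs of special interest and clinically relevant laboratory or ECG abnormalities that are unresolved 7 days after the last dose need not be followed to an outcome. For laboratory abnormalities first seen at Visit 8 the window is about 5 to 7 days with no scheduled repeat, on the protocol's schedule and visit windows.

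Few subjects are likely to be affected. The 30-subject adolescent study reported no treatment-related SAEs and only mild to moderate AEs (Protocol 5.2). The same section gives adult rates of 3% each for raised ALT, AST and alkaline phosphatase and 1% for creatine kinase. Applied to about 45 NFC-1 subjects, these give 45 × 0.03 = 1.35 subjects per liver analyte and 45 × 0.01 = 0.45 for creatine kinase, before asking whether the finding is clinically relevant or late. The rates come from adults at up to 450 mg/day, against 2 × 400 = 800 mg/day here, so they indicate scale only.

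The primary efficacy analysis is untouched. The change is worth making because it is cheap and concerns the events that matter most, not because it would alter a planned result.

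**What to change.** Keep the first sentence of 11.2.5, with all its end points, for ordinary AEs. Then add:

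> The 7-day limit does not apply to SAEs, AEs of special interest (Section 11.3.1) or clinically relevant laboratory or ECG abnormalities with onset or detection during the AE collection period in Section 11.2. These will be followed until resolved, stable, or attributed to another known cause with further evaluation judged clinically unnecessary. The abnormal laboratory test or ECG will be repeated where clinically indicated.

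Add to Section 11.2 that the end of AE collection does not end follow-up or eCRF outcome recording for these ongoing events, and that for subjects who terminate early, collection runs through the 7-day follow-up call. Without this, the whichever-is-first rule in 11.2 would conflict with the new text. Sections 8.3, 10.3.3.1.4 and 10.3.3.2.2 inherit the change through their cross-references.

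The cost is one protocol amendment with sponsor approval, investigator signature and IRB approval (Protocol 14.8), at about 35 sites by Protocol 7.3 or 25 by SAP Section 3, plus occasional extra contacts or repeat standard tests for a few subjects. The existing end points keep follow-up from being open-ended. Repeat results need no SAP change, since SAP 6.1 already lists unscheduled assessments.
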